##### **After the patient terminated the study**

The investigator is responsible for ensuring the follow-up of any patient who experiences:

- an AE related to IMP

- An AESI
- SAE
- An any AE at the investigator's discretion or sponsor's discretion.

until the event has resolved or, any abnormal laboratory values have returned to baseline or stabilized at a level acceptable to the investigator and medical expert or until there is a satisfactory explanation for the changes observed.

#### 6.2.3.5.5 *Management of pregnancy*

In case of the investigator or an appropriate qualified physician is informed that a patient becomes pregnant while taking IMPs, she will be immediately withdrawn from the study and she will be followed until the outcome of the birth is available. Handling of a pregnancy occurring throughout the study follows the same reporting procedure as per an SAE notification.

A communication will be sent by the investigator to Laboratoires THÉA as soon as he/she has knowledge of the normal outcome. Conversely, if the outcome of the pregnancy meets the criteria of SAE (e.g., spontaneous or therapeutic abortion, stillbirth, neonatal death, congenital abnormality, birth defect), the investigator should follow the procedure for reporting of SAEs.

Upon medically confirmed pregnancy during the study the investigator must:

- Report immediately (maximum 24 hours) the pregnancy status to the Sponsor using the email

- Discontinue the IMP for the participant and withdraw the participant from the study
- Perform / ensure assessment until delivery of a thorough study of the fetus
- Remain responsible for any medical advice he/she might seek thus making appropriate decision upon pregnancy,
- Report to the Sponsor follow-up data/update(s) using the SAE form.

This procedure also applies if the female partner of the study patient become pregnant during the study. Then the male patient enrolled in this study should inform the Investigator upon a medically confirmed pregnancy of his partner. If the partner or the caregiver of the newborn consents, data from pregnancy status will be collected and reported thereafter by the investigator. Prior to any data collection, a specific duly designed ICF will be completed.

#### 6.2.3.6 Automated visual field: Standard automated perimetry

Visual field testing in each eye will be performed using the same type of device with the same glaucoma program (24-2 SITA Standard) and evaluation of the visual field defect indices (periodic maintenance is observed according to manufacturer instructions).

At the Visit #1, it will be specified if there is

- an absolute defect in the 10-degree central point
- a severe visual field loss
- a risk of visual field worsening as a consequence of participation in the study.

If AVF is required at Visit #5 or at premature study treatment Discontinuation visit, the investigator will have to indicate if the visual field is stable. If the visual field is not stable, the investigator will have to specify if it is clinically significant or not and will report an AE accordingly.

### 6.2.3.7 Visual acuity

BCVA will be measured in each eye using the same chart (for example a Snellen chart) throughout the study. It can be expressed using units as, LogMAR or Snellen notation. It will be analyzed after conversion in LogMAR (see [Appendix 11.1](#)).

### 6.2.3.8 Gonioscopy: measure of iridocorneal angle

The iridocorneal angle (situated on the circumference of the anterior chamber between the sides of the cornea and sclera and the base of the iris and the anterior surface of the ciliary body) structure will be analyzed with a gonioscope.

At the Visit#1, the IAC will be assessed using grading Schaffer system in 0-5 grades which 4 is wide open and 0 is closed:

- Grade 0: (0°) Closed angle: iridocorneal contact is present (unable to identify the apex of the corneal wedge)
- Slit angle: No obvious iridocorneal contact but no angle structure can be identified; greatest danger of imminent closure
- Grade 1: (10°) Very narrow angle: Schwalbe's line can be identified; angle closure is not inevitable but risk is high
- Grade 2: (20°) Moderately narrow angle: Trabeculum can be identified; angle closure is possible but unlikely
- Grade 3: (25° to 35°) Open angle: Scleral spur can be identified; incapable of closure
- Grade 4: (35-45°) Widest angle: Ciliary body can be visualized with ease; incapable of closure

### 6.2.3.9 Slit Lamp Examination

The following criteria will be assessed with the corresponding scores:

- Conjunctival hyperemia

The level of severity of conjunctival hyperemia will be scored using the [REDACTED] photographic scale (0 to 4) in each eye (see [Appendix 11.3](#)).

- Ocular signs

The following ocular signs will be evaluated in each eye using the slit lamp examination.

- Eyelid examination: eyelid oedema, eyelid erythema, blepharitis
- Conjunctival examination: folliculo-papillary conjunctivitis (after eversion of the superior and inferior eyelids), conjunctival oedema, conjunctival hemorrhage
- Corneal examination: corneal neovascularization, corneal opacity, corneal oedema, cornea verticillata.
- Eyelashes changes
- Iris hyperpigmentation.

in 0-3 scale:

- (0) = None
- (1) = Mild
- (2) = Moderate
- (3) = Severe

– Anterior chamber examination/or Tyndall effect

The following criteria will be assessed in each eye:

Tyndall effect

Cells in field will be scored using the █ Grading Scheme (using 1mm slit beam):

- 0 = < 1 cell
- 0.5+ = 1 to 5 cells
- 1+ = 6 to 15 cells
- 2+ = 16 to 25 cells
- 3+ = 26 to 50 cells
- 4+ = 50+ cells.

Flare will be scored using the █ Grading Scheme (using 1mm slit beam):

- 0 = None
- 1+ = Faint
- 2+ = Moderate (iris/lens details clear)
- 3+ = Marked (iris/lens details hazy)
- 4+ = Intense (fibrin/plastic aqueous).

– Conjunctival lissamine green staining

Nasal and temporal conjunctival staining will be graded in each of the six conjunctival zones following lissamine green instillation using █ scale in each eye █

The score of each zone will be recorded in the e-CRF and in the participant medical record. The total score will be calculated automatically in the e-CRF.

– Corneal fluorescein staining

Approximately 2.5-3.0 minutes following fluorescein instillation, corneal staining will be evaluated in each eye. Fluorescein with and without preservative are authorized. However, the use of preservative-free products is recommended, and the same type of product will be used for the same patient throughout the study. Corneal staining will be scored as following in each of the five corneal zones using the █ scale (A: Central, B: Superior, C: Temporal, D: Nasal, E: Inferior) (█)

0 = Normal, negative slit lamp findings.

1 = Mild, superficial stippling.

2 = Moderate, punctuate staining including superficial abrasion of the cornea.

3 = Severe, abrasion or corneal erosion, deep corneal or recurrent erosion.

The score of each zone will be recorded in the e-CRF and in the participant medical record. The total score (0-15) will be calculated automatically in the e-CRF.

6.2.3.10 Fundus examination

Fundus examination without pupil dilation in each eye.

At the Visit#1: The cup to disk ratio (C/D) will be measured both horizontally and vertically, with the highest value recorded for each eye.

Any abnormality in the posterior segment will also be recorded.

At Visit#5 or premature study treatment discontinuation visit (or at Visit #3 and Visit# 4 if the investigator judges fundus examination will be assessed is necessary) the investigator will indicate if any abnormalities have been detected in the posterior segment. If yes, abnormalities will be specified for each eye.

#### 6.2.3.11 Central corneal thickness measurement

Measurement of the central corneal thickness will be performed with a calibrated ultrasound pachymeter (periodic maintenance is observed according to manufacturer instructions).

The central corneal thickness (in  $\mu\text{m}$ ) will be measured in each eye.

#### 6.2.3.12 CEC assessments

##### CEC assessments at Visit #1 by site

The CEC density (in cell/ $\text{mm}^2$ ) will be assessed in each eye at Visit #1 with a calibrated specular microscopy (periodic maintenance is observed and documented).

##### CEC assessments reviewed by central reading (Visit #2 and Visit #5 or premature treatment discontinuation visit)

The central CEC assessments will be assessed in each eye with the same calibrated specular microscopy (periodic maintenance is observed and documented).

The following parameters will be measured:

- Central CEC density (in cell/ $\text{mm}^2$ )
- Hexagonal cells ratio (in %)
- Coefficient of variation.

Any detected abnormality will be recorded.

Central photographs will be performed in each eye and anonymized photos will be collected. These anonymized photos will be reviewed for assessment by an independent reading center. A dedicated secure transfer supporting CEC assessment data reviewing, analysis and storage might be used: the anonymized photos, values, date and hour of the exam with name of the examiner.

All instructions concerning photos (method, anonymization, storage and reading) will be detailed in a specific study manual.

#### 6.2.3.13 Ocular tolerance assessment by the Investigator

The masked investigator has to answer to the following question:

*“Do you consider the ocular tolerance of the study treatment as?*

- Very satisfactory
- Satisfactory
- Not very satisfactory
- Unsatisfactory”.

#### 6.2.3.14 Ocular tolerance assessment by the patient

The masked investigator has to ask the participant the following question:

*“Do you consider the ocular tolerance of the study treatment as?*

- Very satisfactory
- Satisfactory
- Not very satisfactory

- Unsatisfactory”.

The ocular tolerance will be assessed by the participant.

#### 6.2.3.15 Ocular symptoms immediately after drop instillation

The severity of ocular symptoms **immediately after drop instillation**: will be assessed by the masked Investigator (or masked delegates) asking the patient:

“Have you felt any ocular discomfort/unusual sensation IMMEDIATELY AFTER DROP INSTILLATION since the last visit?”

The following symptoms will be evaluated immediately after IMP instillation:

- Burning/irritation
- Stinging/Eye pain
- Itching/Pruritus
- Ocular redness
- Tearing
- Eye dryness feeling
- Foreign body sensation
- Blurred vision.

Severity will be assessed based on a 4-point scale:

- 0 = Absent,
- 1 = Mild, present but not disturbing
- 2 = Moderate, disturbing
- 3 = Severe, very distressing.

For each symptom, the usual duration and the frequency will be recorded. Frequency will be assessed as follows:

- Very often:  $\geq 80\%$  of instillation/administration
- Often:  $\geq 40\%$  et  $< 80\%$  of instillation/administration
- Not very often:  $\geq 10\%$  et  $< 40\%$  of instillation/administration
- Rarely:  $< 10\%$  of instillation/administration.

These procedures will be assessed globally for both eyes

#### 6.2.3.16 Ocular symptoms throughout the day

The severity of ocular symptoms occurring throughout the day (excluding ocular symptoms immediately after drop instillation) will be assessed by the masked Investigator (or masked delegates) asking the patient:

Visit #2: “How do you judge the severity of the following ocular symptoms throughout the day?”

Visit #3, #4 and #5 or premature study treatment discontinuation: “How do you judge the severity of the following ocular symptoms (excluding ocular symptoms immediately after drop instillation) throughout the day?”

The following symptoms will be evaluated:

- Burning/irritation

- Stinging/Eye pain
- Itching/Pruritus
- Ocular redness
- Tearing
- Eye dryness feeling
- Foreign body sensation.

Severity will be assessed based on a 4-point scale:

0 = Absent  
1 = Mild, present but not disturbing  
2 = Moderate, disturbing, but not limiting with daily activities  
3 = Severe, very distressing and interfering with daily activities.

These procedures will be assessed globally for both eyes.

#### 6.2.3.17 Treatment compliance evaluation

Participant will receive a participant diary after the randomization. Each day from the first to the last IMP instillation participant will record in his/her participant diary:

- Date, time of IMP instillation and eyes instilled.

The patient will return all IMPs whether used or unused at each visit. The number of returned / unreturned IMPs will be recorded in the accountability log by the **unmasked team member**.

The **unmasked team member** will assess compliance by questioning the patient, checking the patient daily diary during the visit (e.g., if there was any treatment interruption or missed instillation) and by the number of used and unused IMPs.

The following information will be reported for each period in the e-CRF:

- Date and time of last IMP instillation
- Missed and daily dose modifications

#### 6.2.4 IMP Complaints

A complaint is defined as any written, electronic, or oral communication that alleges deficiencies related to the identity, quality, durability, reliability, usability, safety, effectiveness, or performance of a product after it is released for distribution. A complaint is any expression of dissatisfaction with a product or service marketed.

If the investigator/patient observes any abnormality and/or complaint of T4090 the investigator must report to [REDACTED] within 24 hours of being aware of it ([Appendix 11.7](#)).

Laboratoires THÉA must

- review all complaint and determine and document in writing whether they could have led to a SAE; in case of disagreement between the sponsor and the principal investigator(s), the Sponsor shall communicate both opinions to concerned parties.
- (if applicable) report to regulatory authorities, IRB, investigators, within the required time period any complaints that might have led to a serious adverse event if appropriate action had not been taken, intervention had not occurred, or circumstances had been less fortunate.

Once Laboratoires THÉA is made aware of any complaint with any components of the IMP and in function of the type of complaint, the Laboratoires THÉA will take the appropriate decision to maintain the security/safety of patient.

## 7 STATISTICAL METHODS

The statistical analysis plan (SAP) will be produced before database lock and breaking the blind detailed methods for the analyses outlined below.

Any changes from the planned analyses will be described and justified in the final clinical study report (CSR).

### 7.1 GENERAL CONSIDERATIONS

Continuous variables will be summarized using descriptive statistics (number of non-missing observations, mean, standard deviation, median, Q1, Q3, minimum and maximum).

Frequency distribution (counts and percentages) will be summarized for the categorical variables.

When applicable, 95% Confidence Interval (CI) of the mean will be provided for continuous variables and 95% CI of the proportion will be displayed for each modality of categorical variables.

Statistical descriptions will be performed by groups. For disposition and demography description will also be presented overall.

Change from baseline could also be presented when necessary.

Variables recorded for each eye will be described separately for the study eye and for the contralateral eye (if applicable).

If not otherwise specified, baseline is defined as the last value before the first instillation for each endpoint.

The mean diurnal IOP at Day 1 will be the baseline for analysis of the mean diurnal IOP. For IOP, the value recorded at 8:00 AM at Day 1, respectively at 10:00 AM and at 4:00 PM, will be the baseline for analysis of IOP at 8:00 AM, respectively at 10:00 AM and at 4:00 PM.

Comparison between groups will be performed at a two-sided significance level of 5% and no adjustment of the type I error rate will be made.

### 7.2 ANALYSIS SETS

The following analysis sets will be considered:

- **Safety set:**

All enrolled patients, having received at least one dose of IMP and considered as-treated.

– **Intent-to-Treat (ITT) set:**

All randomized patients.

– **Full-Analysis Set (FAS):**

All randomized patients having received at least one dose of IMP.

– **Per-Protocol (PP) set:**

All FAS patients without any major protocol violation (likely to seriously affect the primary outcome of the study).

[REDACTED]

Safety set will be the primary population for safety analysis.

FAS set will be the primary population for efficacy analysis.

The PP set will be considered as secondary population and will be used for sensitivity analyses of the primary and secondary efficacy endpoints.

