**Investigator-masked:**

A double-masked study design was not feasible due to the different packaging between T4090 and Rhopressa (SDC *versus* MDC).

To obtain unbiased data, investigator-masked study is designed, meaning that the masked investigator or masked authorized collaborator, in charge of ophthalmic examinations are not aware of the allocated treatment.

To respect this constraint, the following precautions will be taken:

- **Masked and unmasked teams** will be assigned. The role and responsibilities of masked and unmasked site staff will be further described in the Study Personnel Delegation Form. The same masked investigator must attend all study visits from randomization visit to the last visit for the same patient.

During the whole study treatment period the **masked investigator** or **other masked qualified site staff** per local regulation (=**designee**), in charge of ophthalmic examinations (including IOP measurement) will not be aware of the allocated treatment (T4090 or Rhopressa). He/she will not deliver, nor receive the returned medication from the patient and will be trained not to discuss IMP with patients.

- IOP measurements will be performed by two persons: the **masked Investigator/designee** (same for all visits from Randomization visit onwards) reaches the correct applanation effect in the slit lamp and **must be masked to the readout** of the tonometer during the measurements. A second staff member reads and transcribes the IOP values (readout of the

tonometer) into the patient source document once the masked Investigator/designee reaches the correct applanation effect in the slit lamp.

- Each site must have at least one **unmasked team member** dedicated to IMP management (e.g. Unmasked Investigator and /or Pharmacist or other qualified site staff/designee per local regulation). This **unmasked team member** does not participate in the evaluation of patients, after first IMP dispensation and does not communicate any unmasking information with the masked teams.
- Final packaging of IMP will be identical in external appearance to respect the masking: same final packaging, same weight, and dividers to avoid boxes or aluminum pouches to move.
- Instructions will be given to the patient in the informed consent form (ICF)/patient's brochure that she/he must not return used/unused IMP to masked investigator/designee.

[figure not shown]

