## 5.1.5 Dispensing and Return

### 5.1.5.1 Dispensing

The IMPs must be dispensed only to patient in accordance with the protocol and the randomization.

At the Randomization visit (D1), once selection criteria have been checked and once the patient is eligible, the randomization will be performed, and an IMP number will be allocated to the patient.

IMP will be delivered by the **unmasked team member**. Each IMP dispensation will be recorded in the related unmasked documentation.

During the whole study treatment period, the **masked investigator** will remain masked to the IMP (T4090 or Rhopressa). He/she will not deliver or receive the returned medication from the patient and will be trained not to discuss IMP with patients.

All information regarding the usage of the IMPs will be given to patients and will be explained by the **unmasked investigator**.

During the study, three deliveries will be performed as follow:

- At Randomization visit (D1): one box containing enough medication for the treatment period D1 to W2 with the daily diary associated to this period will be provided to the patient by the **unmasked team member** with the number assigned by the IRT
- Visit #3 – W2: resupply of one box containing enough medication for the treatment period W2 to W4 with the daily diary associated to this period, will be provided to the patient by the **unmasked team member** with the number assigned by the IRT
- At Visit #4 - W4: resupply of one box containing enough medication for the treatment period W7 with the daily diary associated to this period, will be provided to the patient by the **unmasked team member** with the number assigned by the IRT.

A record of the IMP dispensed to the patient will be maintained by the **unmasked team member** in the patient unmasked medical records and the accountability log.

The **unmasked team member** will instruct patients not to discuss IMP with the **masked investigator** and on method of instilling the doses:

- Treatment period: IMP (T4090 or Rhopressa) will be instilled by the patient one drop in each eye once daily at 8:00 PM ( $\pm 1$  h).

This is crucial to maintain the blind and avoid any accidental unmasking.

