5.2. Intent-to-Treat Set [ITT]

The intent-to-treat (ITT) set will contain all patients who were randomized. For analyses and displays based on ITT, patients will be classified according to randomized treatment.

Document: ...\\Biostatistics\\Documentation\\SAP\\ T4090-201_Statistical Analysis Plan_V1.0

Author: [REDACTED] Version Number: 1.0

Version Date: 13Nov2024

Statistical Analysis Plan

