5.3. Full Analysis Set [FAS]

The full analysis set (FAS) will contain all patients in the ITT set who received at least one dose of study treatment. For analyses and displays based on FAS, patients will be classified according to randomized treatment.

The FAS will be the primary population for efficacy analysis.

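### The primary efficacy set omits randomised patients who never take a dose, and that omission can depend on the arm for T4090 versus Rhopressa

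*Protocol*

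**What the plan says.** **Analysis sets.** Protocol 7.2 defines the ITT set as "All randomized patients" and the FAS as "All randomized patients having received at least one dose of IMP". SAP 5.2 and 5.3 match this: "The intent-to-treat (ITT) set will contain all patients who were randomized", whereas "The full analysis set (FAS) will contain all patients in the ITT set who received at least one dose of study treatment". Both documents make the FAS primary for efficacy (in Protocol 7.2, "FAS set will be the primary population for efficacy analysis"), and SAP 16.1.3 runs the primary MMRM on it. The only other efficacy set in the readable text is the PP set, which "will be used for sensitivity analyses of the primary and secondary efficacy endpoints" (Protocol 7.2). The PP set lies inside the FAS. The readable text uses the ITT set only for the table of set membership (SAP 9.1) and the protocol-deviation outputs (SAP 9.2).

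**Masking and first dose.** Protocol 3.2 explains that "A double-masked study design was not feasible due to the different packaging between T4090 and Rhopressa". In the order listed for Visit #2 (Protocol 6.1.2), randomisation follows the IOP readings, the last of which is at 4:00 PM. An unmasked team member then dispenses the product and explains its use. The product "will be instilled by the patient one drop in each eye once daily at 8:00 PM" (Protocol 5.1.5.1), starting on Day 1 (Protocol 3.1.2).

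**Follow-up.** Protocol 4.4.3 keeps patients in the visit schedule to Week 7 after they discontinue study treatment. Section 4.4.1 describes permanent discontinuation as a decision against re-exposure, which presupposes exposure. Neither section mentions a patient who never starts. Section 4.5 does foresee such patients: a randomised patient who leaves keeps the randomisation number whether or not IMP was taken.

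**The concern.** Leaving out never-dosed patients is harmless when the decision to start cannot depend on the assigned arm, as in a fully masked trial. That condition is not met here. The patient learns the container type after randomisation and before the first self-administered drop. A patient who is put off by the presentation can decline to start and then drops out of the primary analysis.

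The masked IOP assessor protects the measurement, not this decision. Agreeing set membership before unblinding (SAP 5) prevents selection by analysts, not by patients. At stake is whether each T4090 versus Rhopressa difference at Week 7 is estimated on the groups that randomisation formed. The PP analysis cannot help, because it starts from the same reduced set.

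**Working it through.** **1. The plan's own allowance.** Protocol 4.1 plans 126 randomised patients to obtain 120 evaluable, allocated 1:1:1 (Protocol 4.5).
- Per arm: 126/3 = 42 randomised and 120/3 = 40 evaluable.
- Implied loss: (126 − 120)/126 = 4.8%, which is 6 patients in all or 2 per arm. As a check, 120 × 1.05 = 126.
- Evaluable means dosed and with all three IOP timepoints at one visit after randomisation. The 6 therefore also cover dosed patients without a complete visit, and never-dosed patients can be only part of them.

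**2. Shift in an arm mean.** Let k be the number of never-dosed patients in an arm of 42, all with Week 7 mean diurnal IOP. Let D be the difference between their mean change and that of the dosed patients. Putting them back moves the arm mean by (k/42) × D. The documents give no value for k or D; D = 2 to 6 mmHg is assumed.

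| k | share of arm | shift at D = 2 | shift at D = 4 | shift at D = 6 |
|---|---|---|---|---|
| 1 | 2.4% | 0.05 | 0.10 | 0.14 |
| 2 (per-arm allowance) | 4.8% | 0.10 | 0.19 | 0.29 |
| 6 (whole allowance in one arm) | 14.3% | 0.29 | 0.57 | 0.86 |

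Shifts are in mmHg. The sign of D is not known: after stopping study treatment a patient may receive other antiglaucoma treatment (Protocol 4.4.3).

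**3. Precision for comparison.** Neither document gives an SD, and no formal sample size calculation was made (Protocol 7.5). With an assumed SD of 2.5 to 4 mmHg and 40 per arm, and ignoring the gain from baseline adjustment:
- SE = SD × √(2/40) = 0.56 to 0.89 mmHg.
- 95% CI half-width = 1.96 × SE = 1.10 to 1.75 mmHg.

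A shift of 0.10 to 0.29 mmHg is well inside this. Even the extreme of 0.86 mmHg is below the half-width.

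**4. What relabelling the set would do.** The MMRM uses post-baseline visits, and mean diurnal IOP is missing if any of the three timepoints is missing (SAP 16.1.1). A never-dosed patient who does not return has no such value and adds nothing to the likelihood. For such patients, a model run on the ITT set gives the same estimate as one run on the FAS. The sets give different results only if never-starters attend.

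**5. Which comparisons are exposed.** Both T4090 strengths come in single-dose containers and Rhopressa in a multiple-dose container (Protocol 3.1.2). Knowing the container separates T4090 from Rhopressa but not 0.2% from 0.3%.

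**The case against.** The strongest defence has four parts.

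- **The exclusion will be visible.** SAP 9.1 tabulates membership of each set, with reasons for exclusion, by treatment group on the ITT set. This stands: an imbalance in never-dosed patients would be seen. The table shows the imbalance but does not estimate its effect on IOP.
- **The mechanism is not demonstrated.** Patients have consented, pre-treated patients have completed a washout, and all have sat through three IOP readings on Day 1. A reader might infer that arm-dependent exclusion will occur. The documents show only that it can. That the first drop is taken at home is itself inferred from self-dosing at about 8:00 PM with a diary.
- **The FAS suits the estimand.** Protocol 7.3.1.1 describes products as administered, and 7.3.1.4 confines intercurrent events to those after treatment initiation. This stands in part. But the target population in 7.3.1.2 is set by diagnosis and eligibility, not by having taken a dose, so a never-starter belongs to the population and is still outside the primary analysis.
- **Text is redacted.** A reader might infer that no ITT efficacy analysis is planned. The documents do not support that. Parts of Protocol 7.2, 7.3.1.4 and 7.4.1.1 and of SAP 3.4, 5 and 16 are withheld, and an ITT sensitivity analysis could be there. All that can be said is that none appears in the readable text.

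**Conclusion.** The point holds as a minor one. Entry to the primary efficacy set is settled after randomisation by a patient who can know whether the product is T4090 or Rhopressa, so those two comparisons are not fully protected by randomisation. It would be wrong to extend this to the comparison of the two T4090 strengths.

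The likely size is 0.10 to 0.29 mmHg in an arm mean if a full per-arm allowance of 2 patients never started, against a CI half-width of 1.10 to 1.75 mmHg. This rests on assumed values of D and SD, on an assumed number of never-starters, and on those patients having Week 7 IOP. If every randomised patient takes a dose, the ITT set and the FAS coincide and nothing is lost. The trial is exploratory (Protocol 7.5) and its tests are treated as supportive (SAP 7.5), which limits the consequence. Its results are still meant to inform the Phase III design (Protocol 3.2), so a comparison on the randomised groups is worth its small cost.

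**What to change.** Make both changes together, since the second adds no data without the first.

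1. In Protocol 4.4.3, state that a randomised patient who never starts IMP is also asked to attend the scheduled visits to Week 7.
2. In Protocol 7.2 and 7.4.1.1 and SAP 5.3 and 16.1.3, run the same MMRM on the ITT set by randomised arm, using every randomised patient with post-baseline mean diurnal IOP. Make it the primary analysis with the FAS as supportive. If the FAS stays primary, pre-specify the ITT run as a sensitivity analysis of the two T4090 versus Rhopressa comparisons. If the redacted text already contains this run, only the first change is needed.

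The cost is a sentence in the protocol, some SAP wording and one more run of an existing model, on visits already in the schedule. The downside is a slightly diluted treatment estimate if some patients never start.
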